Study Protocol for:

Development and Pilot Trial of an Intervention to Reduce Disclosure Recipients Negative Social

Reactions and Victims Psychological Distress and Problem Drinking

NCT03488927

Last approved August 25, 2020

Contents:

Study Protocol

Research Design

Participants were assigned to either the treatment condition or the wait-list control condition. Because a large number of participants ($n = 531$; 63.50% of participants invited) who were assigned to the treatment condition did not attend the actual intervention, we created three groups for the purposes of analyses: control ($n = 432$), treatment attender (Tx-Attender; $n = 305$), treatment non-attender (Tx-Nonattender; $n = 531$).

Procedures

The study took place at a residential, medium-size public university in the northeastern United States and received approval from the university's Institutional Review Board. The university's Dean of students sent emails to randomly selected, full-time, undergraduate students between the ages of 18 and 24 on the behalf of the researchers. These emails (initial and two reminders) were sent via mass email to 7,000 students in four batches across four weeks in the fall of 2018. We also sent an email from the research team to all professors at the University with classes greater than 60 students ($n = 205$ professors), as identified by the course catalog. Lastly, we posted fliers in residence halls and other shared spaces about the study.

Overall, 1,831 students started the baseline survey, of whom 1,268 consented to and completed the survey. Of our final 1,268 participants, 78.4% ($n = 994$) were recruited via official email from the Dean of students, 14.4% ($n = 183$) were recruited via a friend (i.e., a friend forwarded the study information), 4.9% ($n = 62$) were recruited via professors, 1.3% ($n = 16$) were recruited via fliers, 0.6% ($n = 8$) were recruited via the website, and 0.4% ($n = 5$) were recruited in another way (e.g., "Facebook"). Qualtrics randomized participants into intervention and control groups. Participants were initially randomized at a 50/50 rate to the intervention and control conditions. However, we found that rates of intervention attendance were lower than

expected. Thus, in order to achieve desired numbers of intervention participants, when we reached over 400 in the control group, we began assigning 100% of participants who were randomly selected to be emailed to the intervention group. Because participants were recruited via professors and fliers were not randomly selected, these participants were randomized 50/50. Thus, 65.9% of participants were assigned to the intervention ($n = 836$) and 34.1% were assigned to control ($n = 432$). Participants randomized into the intervention group were invited to attend the intervention, which was conducted in two sessions (initial session and booster session). Initial session attendance was 36.2% ($n = 303$); of those, 83.1% ($n = 252$) attended the booster.

Participants first completed the baseline survey (Time 1). An average of two weeks later, those in the intervention group participated in the first intervention session. The follow-up survey (Time 2) occurred 6 months after the first intervention session, and, for control participants, 6 months and 2 weeks after their baseline survey (to ensure receipt of email at times comparable to intervention participants). We sent participants up to eight total text, email, and call reminders to remind them of the Time 2 survey. Of the 1,268 baseline participants, 70.1% ($n = 889$) completed the Time 2 survey, including 314 in the control condition and 575 in the intervention group. Participants received \$15 and \$25 gift cards for completing Time 1 and 2, respectively. Of the 305 participants who attended the first session, 252 (82.6%) attended the booster session. Participants also received reminder texts, emails, and calls to remind them about the initial and booster sessions; they received up to five of these reminders.

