**Analysis Plan for:**

**Development and Pilot Trial of an Intervention to Reduce Disclosure Recipients Negative Social**

**Reactions and Victims Psychological Distress and Problem Drinking**

**NCT03488927**

**Last approved August 25, 2020**

**Contents:**

**Analysis Plan**

## Analysis Plan

**Main effects.** Treatment effect analyses compared participants in the intervention group who attended (Tx-Attender;  $n = 305$ ) to both: (a) participants who were invited to the treatment but who did not attend (Tx-Nonattender;  $n = 531$ ) and (b) participants in the control group ( $n = 432$ ). We conducted ANCOVA analyses in SPSS. We added contrasts to compare the three groups using the /LMATRIX subcommand. Covariates included gender, year in college, and alcohol use in the past 30 days, based on baseline differences in these variables. We used these covariates for all models except those models including alcohol use frequency or binge drinking as moderators, where we only included gender and year in college (because there was no variability in alcohol use in the past 30 days with these moderators).

Dependent variables differed by hypothesis. To test Hypothesis 1, we compared the three groups on T2 intended reactions, among participants who responded about intentions at T2 ( $n = 415$ ). To test Hypothesis 2, we compared the three groups on T2 actual reactions, among participants who responded about actual reactions at T2 ( $n = 474$ ). To test Hypothesis 3, we compared the T2 scores on intermediary variables of all participants, with the T1 score of each outcome as a covariate to assess for differences in change.

**Moderation analyses.** We explored four categories of moderators: demographic, IPV/SA, alcohol use, and characteristics of actual disclosures. To explore moderation, intervention condition was operationalized via two dummy codes: Tx-Attender (1) vs. Control (0) and Tx-Attender (1) vs. Tx-Nonattender (0). We then entered these dummy-coded variables into a regression model in SPSS along with covariates consistent to the covariates in the main effect analysis, main effect of the moderator, and the two interactions of interest (i.e., interaction between each dummy-coded treatment variable and moderator). For example, for gender, we

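### An inferred 404 or so of the 836 intervention participants had no chance of being control, and the contrasts with Control do not fully account for that change in allocation

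*Protocol*

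**What the plan says.** **Protocol, Procedures.** Allocation began evenly: "Participants were initially randomized at a 50/50 rate to the intervention and control conditions". Attendance was lower than hoped, so the rule changed "in order to achieve desired numbers of intervention participants, when we reached over 400 in the control group". From then on, "we began assigning 100% of participants who were randomly selected to be emailed to the intervention group". Two recruitment streams were exempt: those reached through professors and "fliers were not randomly selected, these participants were randomized 50/50". A further 183 people "were recruited via a friend (i.e., a friend forwarded the study information"), 8 came through the website and 5 by other routes; the Protocol does not say how these 196 were assigned after the switch. Invitation emails were "sent via mass email to 7,000 students in four batches across four weeks in the fall of 2018". The end result was 836 intervention and 432 control, with 889 completing T2, "including 314 in the control condition and 575 in the intervention group".

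**SAP, Main effects.** "Treatment effect analyses compared participants in the intervention group who attended" with invited non-attenders and with controls, by ANCOVA. The covariates are gender, college year and past-30-day drinking, chosen because they differed at baseline. Hypothesis 3 adds the T1 score; no T1 score is stated for Hypotheses 1 and 2. The moderation models carry the same covariates, with drinking dropped for two alcohol moderators. No model has a term for enrolment date, email batch or allocation period. No analysis is restricted to participants allocated 50/50, and none compares the arms as assigned.

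**The concern.** After the switch, a directly emailed participant could only enter the intervention. Control is therefore almost wholly an early-enrolment group, while roughly half of the intervention arm enrolled late. Any early/late difference that the covariates miss enters Tx-Attender versus Control as if it were an effect of treatment. The same would happen in a simple 836 versus 432 comparison, so adding an intention-to-treat analysis without a restriction would not remove it. Tx-Attender versus Tx-Nonattender is not affected through assignment, since both groups come from the intervention arm.

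The documents give neither the switch date nor counts before and after it, so a reader cannot judge the size of the problem. The plan as written also has no estimate that rests on randomisation.

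**Working it through.** **Plan's own figures.** 836 + 432 = 1,268; 836/1,268 = 65.9% and 432/1,268 = 34.1%, as stated. The sources also add up: 994 + 183 + 62 + 16 + 8 + 5 = 1,268.

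**How many had no chance of control.**
- Under 50/50 allocation, 432 controls imply about 432 intervention participants. The excess is 836 - 432 = 404, or 404/836 = 48.3%. This does not depend on the exact switch point.
- Under simple randomisation, the number of intervention participants drawn alongside 432 controls is negative binomial (432, 0.5), with 95% limits 376 to 491. The excess is then 836 - 491 = 345 to 836 - 376 = 460. If the software balanced the arms, it is close to 404.
- Directly emailed: at most 404, and at least 404 - (183 + 8 + 5) = 208. The chance range widens this to 345 - 196 = 149 up to 460. The low ends require all 196 friend, website and other recruits to have enrolled after the switch and all to have gone to the intervention, which is extreme.
- Late controls: at most 432 - 401 = 31.
- Source mix by arm cannot be recovered. If all 274 non-email recruits were split evenly, email recruits are (432 - 137)/432 = 68% of control and (836 - 137)/836 = 84% of intervention. If all 196 went to the intervention, the figures are 393/432 = 91% and 601/836 = 72%.

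**Type I error, Tx-Attender versus Control.** Let d be the early/late difference left after covariates, in SD (assumed), and b the late share among attenders minus that among controls. Bias is b × d, and type I error is P(|Z + b·d/SE| > 1.96).
- Attenders at T2 are not reported. Equal retention (assumed) gives 305 × 575/836 = 210, so SE = √(1/210 + 1/314) = 0.089. Splitting H1 (415) and H2 (474) in the same shares gives 98 versus 147 (SE 0.131) and 112 versus 167 (SE 0.122).
- With no late controls and attendance unrelated to period, b = 0.483. With 31 late controls, b = 435/836 - 31/432 = 0.520 - 0.072 = 0.449.

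| d | All 889 completers | H1 | H2 |
|---|---|---|---|
| 0.05 | 5.8% | 5.4% | 5.4% |
| 0.1 | 8.4% | 6.6% | 6.8% |
| 0.2 | 19% | 11.5% | 12.4% |

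(b = 0.483; with b = 0.449 the last row is 17.2%, 10.6% and 11.4%.)

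- With 150 to 305 attenders at T2 (assumed range), the 19% becomes 16-23%.
- If late attendance was 0.5 to 1.5 times early attendance, with 0 to 31 late controls, b runs from 0.28 to 0.58. Type I error reaches 10% when b·d/SE is about 0.65. For all completers that is d = 0.65 × 0.089/0.58 = 0.10 up to 0.65 × 0.089/0.28 = 0.21; for H1/H2 it is 0.14 to 0.30.
- Since 415 + 474 = 889, the full-completer size is that of H3, which adjusts for T1. If the drift is equally present at T1 and T2, with correlation ρ (assumed), bias is b·d(1 - ρ) and the SE is multiplied by √(1 - ρ²). The 19% then falls to 9.6% (ρ = 0.5) or 7.4% (ρ = 0.7).

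**The case against.** The strongest reply is that no harm is shown. The documents give no evidence of drift. Emailed students were randomly selected and the mailings ran over four weeks, so early and late respondents may be much alike. At drift of 0.05 to 0.1 SD the error rate hardly moves. The covariates were chosen from observed baseline differences and will absorb drift that shows in them; the T1 score in H3 does more. All of this stands, and it is why the point is not rated higher. It does not settle the matter: random selection for email does not make prompt and late responders alike, it does not cover friend referrals, and covariates picked from observed differences do not model a known change in allocation.

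A second reply is that self-selection dominates, because 531 of the 836 invited did not attend. That too is fair. Tx-Attender versus Control would be non-randomised even with perfect allocation.

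Three stronger readings are tempting, and the documents support none of them. A reader might infer that all 404 were directly emailed, but the unstated rule for 196 recruits prevents that. A reader might infer that the Control contrasts take no account of early/late differences at all, but they do so in part. A reader might take 19% as the trial's actual error rate, but that figure needs a 0.2 SD residual drift that nothing in the documents establishes.

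**Conclusion.** The point holds as a matter of design and reporting, and should be fixed. The switch is stated outright. About 404 of 836 intervention participants (345 to 460 by chance) had no chance of being control, an inference from the final counts. The contrasts with Control neither model the switch nor restrict to participants allocated 50/50.

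Confidence is high that the switch occurred and is not modelled, and low about its consequence. Direction and size of bias cannot be derived from the documents. Depending on late controls and attendance by period, drift of about 0.10-0.21 SD (all completers) or 0.14-0.30 SD (H1/H2) is needed before type I error reaches 10%. These figures rest on assumed drift, assumed retention of attenders and assumed H1/H2 splits; the 404 needs none of those.

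**What to change.** The SAP describes analyses already done, so label all additions post hoc. The cost is wording and a re-run with no new data, provided survey timestamps can be recovered (assumed).

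1. **Add an assigned-arm comparison for H1-H3 restricted to a documented 50/50 chance:** everyone before the switch, professor and flier recruits after it, and other recruits after it only if records show they were randomised. Give the pooled 1,268 as sensitivity, and state that both are conditional on T2 response.
   - Pooled SE is √(1/314 + 1/575) = 0.070. Restricted, with 432 × 575/836 = 297 intervention completers, it is √(1/314 + 1/297) = 0.081, about 15% wider (12-20% over the chance range).
   - The 95% half-width is 1.96 × 0.081 = 0.16 SD for all completers, 0.23 for H1 and 0.22 for H2. Attendance is 305/836 = 36.5%. With no effect in non-attenders (assumed), the interval excludes zero only for attender effects above about 0.43 SD overall, 0.60 for H2 and 0.63-0.64 for H1 (unrounded half-width divided by 0.365). Say so, and report the interval.
   - This does not repair the Tx-Attender contrast.

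2. **Keep the planned models and repeat Tx-Attender versus Control once with a before/after-switch indicator, as sensitivity only.** State that the period effect is estimated almost wholly within the intervention arm and assumed equal across groups. Weighted least squares on the assumed T2 cells (Control 314, Attender 210, Nonattender 365, each split by its late share) raises the SE from 0.089 to 0.096-0.098, about 7-10%. Mean squared error improves only if drift exceeds about 0.08 SD (all completers) or 0.11-0.12 SD (H1/H2), so it should not replace the planned model.

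3. **Report** the switch date, how friend, website and other recruits were assigned after it, and counts by arm, source and period.

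### Delivery format is not stated; if attenders shared sessions or facilitators, the ANCOVA ignores one-arm clustering and the Tx-Attender standard errors could be too small

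*Protocol*

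**What the plan says.** **Allocation and delivery (protocol, Research Design and Procedures).** Allocation was by individual: "Qualtrics randomized participants into intervention and control groups". The comparator was a wait-list: "Participants were assigned to either the treatment condition or the wait-list control condition". Those allocated to the intervention "were invited to attend the intervention, which was conducted in two sessions (initial session and booster session". On attendance: "Of the 305 participants who attended the first session, 252 (82.6%) attended the booster session"; the same section also gives 303 as the initial-session count. No group size, number of session runs, mode of delivery or number of facilitators is given.

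**Follow-up (protocol, Procedures).** Time 2 completers are reported by assigned arm, "including 314 in the control condition and 575 in the intervention group". The number of attenders among the 575 is not given.

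**Analysis (SAP, Main effects and Moderation analyses).** The main-effect method is an ordinary fixed-effects model: "We conducted ANCOVA analyses in SPSS". Group comparisons are specified within that model: "We added contrasts to compare the three groups using the /LMATRIX subcommand". The adjustment set holds three participant-level variables and nothing about delivery: "Covariates included gender, year in college, and alcohol use in the past 30 days, based on baseline differences in these variables". For Hypothesis 3 the Time 1 score of the outcome is added. Moderation uses regression with two dummy codes, each setting Tx-Attender against one of the other groups. Neither document mentions a session or facilitator term, a random effect or a cluster-robust variance.

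**The concern.** Only attenders received the intervention before Time 2. Wait-list controls have no sessions described before then, and Tx-Nonattenders attended none by definition. Any correlation created by delivery therefore falls on one group of the three.

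Two routes are possible. Group sessions would nest attenders in sessions; one-to-one sessions run by several people would nest them in facilitators. In either case outcomes of attenders who shared a session or facilitator may be positively correlated. The attender mean is then less precise than an ordinary ANCOVA assumes.

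Both named main-effect comparisons and both moderation codes have Tx-Attender on one side, so all of them are exposed. At stake are the width of the confidence intervals and the false-positive rate of the treatment claims. A reader also could not tell whether an apparent effect depended on who delivered the sessions.

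**Working it through.** The documents give no alpha, power calculation, ICC, cluster size or standard error, so there is no planned figure to reproduce. What follows is a sensitivity calculation for the main-effect contrasts.

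**Inputs from the documents:** 305 attenders, 836 assigned to the intervention, 432 controls and 1,268 in all at baseline; 314 controls and 575 intervention participants at Time 2; 415 analysed for Hypothesis 1 and 474 for Hypothesis 2.

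**Assumptions not in the documents**
- Two-sided 5% nominal level, with a large-sample normal reference and no penalty for few clusters.
- Attenders were retained at Time 2 at the rate of their whole arm: 305 × 575/836 = 210. That leaves 575 − 210 = 365 non-attenders.
- The Hypothesis 1 and 2 sets split in proportion to baseline group sizes. Hypothesis 1: 415 × 305/1,268 = 100 attenders and 415 × 432/1,268 = 141 controls. Hypothesis 2: 474 × 305/1,268 = 114 and 474 × 432/1,268 = 161.
- m = 5 to 15 Time 2 responders per session; ICC = 0 to 0.10.

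**Formulas**, with clustering in the attender group only (n_A attenders, n_C comparators):
- Design effect: DE = 1 + (m − 1) × ICC
- SE ratio: R = √[(DE/n_A + 1/n_C) / (1/n_A + 1/n_C)]
- True level = 2 × [1 − Φ(1.96/R)]

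**Hypothesis 3, Tx-Attender (210) versus Control (314), session clustering**

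| m | ICC | DE | R | True level |
|---|---|---|---|---|
| any | 0 | 1.00 | 1.000 | 5.0% |
| 5 | 0.02 | 1.08 | 1.024 | 5.6% |
| 10 | 0.05 | 1.45 | 1.127 | 8.2% |
| 15 | 0.10 | 2.40 | 1.356 | 14.8% |

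Worked row: m = 10, ICC 0.05 gives DE = 1 + 9 × 0.05 = 1.45. Then R = √[(1.45/210 + 1/314) / (1/210 + 1/314)] = 1.127, and 2 × [1 − Φ(1.96/1.127)] = 8.2%. Tx-Attender versus Tx-Nonattender (210 versus 365) is similar: R = 1.134 and 8.4% in the same scenario.

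**Hypotheses 1 and 2, same scenario.** Fewer attenders answered, so each session contributes fewer responders.
- Hypothesis 1: m = 10 × 100/210 = 4.76; DE = 1 + 3.76 × 0.05 = 1.188; R = 1.054; true level about 6.3%.
- Hypothesis 2: m = 10 × 114/210 = 5.43; DE = 1 + 4.43 × 0.05 = 1.221; R = 1.063; true level about 6.5%.

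**Facilitator clustering, Hypothesis 3**, with m = 210/k for k facilitators (k and ICC assumed):
- k = 10, ICC 0.01: m = 21, DE = 1.20, R = 1.058, true level 6.4%.
- k = 4, ICC 0.05: m = 52.5, DE = 3.575, R = 1.595, true level 21.9%.

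**Unaffected contrast.** Tx-Nonattender versus Control has no sessions on either side, so DE = 1 in both groups. The moderation interactions were not quantified: their inflation also depends on how each moderator varies within sessions.

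**The case against.** The strongest reply is that the documents never show shared delivery. A reader might infer group sessions from the phrase about two sessions, and conclude that the standard errors are probably too small. The text does not support that. It describes two occasions per participant, an initial session and a booster, and is silent on groups and facilitators. About 305 initial and 252 booster attendances make shared sessions or several facilitators plausible, but that is inference. One facilitator seeing everyone individually, or self-administered delivery, would leave nothing to correct. This part of the reply stands: the claim must be conditional, and its range must include no inflation.

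It is also fair that the larger figures belong to Hypothesis 3, on intermediary variables. Hypotheses 1 and 2, on intended and actual reactions, use fewer responders, and their inflation under session clustering is smaller. The 21.9% case needs four facilitators and ICC 0.05, neither of which is documented.

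Finally, attenders are a self-selected part of the assigned arm, and a corrected standard error does not turn their contrasts into randomized comparisons. That is true, and arguably the larger problem, but it does not make an independence assumption right if delivery was shared. The SAP neither states the format nor makes any provision for clustering, and that omission is what remains.

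**Conclusion.** The point holds conditionally. The analysis assumes independent participants, and the documents omit the facts needed to judge that assumption for the one group that attended sessions. If sessions or facilitators were shared, standard errors of the Tx-Attender contrasts could be too small.

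For Hypothesis 3 against Control, the understatement by session clustering runs from none to a factor of about 1.36. A nominal 5% test would have a true level between 5.0% and about 15%. Few facilitators could push it higher. These figures depend on the assumed session size, ICC and attender count at Time 2. Using 303 attenders instead of 305 would barely move them (303 × 575/836 = 208). The documents do not establish that inflation occurred, only that the plan would not account for it.

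**What to change.** State the delivery format, the number and size of sessions and the number of facilitators. Take first-session and facilitator identifiers from the attendance records, then:

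- **Group sessions:** replace the ANCOVA and moderation regressions with a partially nested mixed model. Keep the same fixed effects and contrasts, add a random session intercept for Tx-Attenders only, and use Satterthwaite or Kenward-Roger degrees of freedom.
- **One-to-one delivery by several facilitators:** use the same model with facilitator as the attender-only random level.
- **Too few facilitators to estimate that variance:** report results by facilitator and state that facilitator correlation has not been removed. A session intercept would not remove it.
- **Neither shared:** keep the ANCOVA and say why in one sentence.

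The cost is somewhat wider confidence intervals and, because the SAP reports its analyses in the past tense, a re-run rather than rewording alone. It depends on the identifiers having been recorded, which the documents do not show. If the estimated cluster variance is zero, the result is close to the planned ANCOVA. The change does not address self-selection of attenders.

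### Does the conflict between 303 and 305 first-session attenders, with no formal definition of Tx-Attender, call for a change to the plan?

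*Protocol*

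**What the plan says.** Procedures in the Protocol describes an intervention "which was conducted in two sessions (initial session and booster session". Its paragraph on recruitment and randomisation ends: "Initial session attendance was 36.2% ($n = 303$); of those, 83.1% ($n = 252$) attended the booster". The closing paragraph of the same section says: "Of the 305 participants who attended the first session, 252 (82.6%) attended the booster session".

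Research Design in the Protocol forms the analysis groups because many people "who were assigned to the treatment condition did not attend the actual intervention" ("n = 531$; 63.50% of participants invited"). It gives the two intervention groups as "treatment attender (Tx-Attender; $n = 305$), treatment non-attender (Tx-Nonattender; $n = 531", beside 432 controls.

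The SAP, under Main effects, compares "participants in the intervention group who attended (Tx-Attender; $n = 305$ ) to both" the controls and those described as "participants who were invited to the treatment but who did not attend", with the same three group sizes. Neither document has a sentence that defines an attender by session.

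**The concern.** Two counts are given for one event in one arm, and both cannot be true. Attendance is also more than a descriptive statistic here. It separates Tx-Attender from Tx-Nonattender in the ANCOVA contrasts and in the two dummy codes of the moderation models. The intervention had two sessions, yet the group descriptions say only that people attended or did not. If 303 were the right first-session count, a reader could ask on what basis the other two people are in a group of 305, and whether they belong with the non-attenders. At stake are the reported attendance and booster rates, the reproducibility of the grouping and, in the worst case, the placement of two people in every contrast.

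**Working it through.** **Inputs.** From Protocol, Procedures: 836 assigned to intervention, 432 to control, 1,268 in total; first-session attendance 303 (36.2%) or 305; booster attendance 252 (83.1% or 82.6%); 575 of the 836 with Time 2 data, 889 overall. From Research Design and the SAP: groups of 305, 531 and 432. From the SAP: 415 people in the Hypothesis 1 analysis.

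**1. Reproduce the stated percentages.**
- 303/836 = 36.24%, stated as 36.2%. A value rounding to 36.2% needs a count between 302.2 and 303.05, so only 303 fits. 305/836 = 36.48%.
- 252/305 = 82.62%, stated as 82.6%. That needs a denominator between 304.9 and 305.3, so only 305 fits.
- 252/303 = 83.17%, which rounds to 83.2%. The stated 83.1% is off in its last digit.
- 531/836 = 63.52%, stated as 63.50%. To one decimal this is 63.5%, which only 531 gives; 533/836 = 63.76%.

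Each count goes with its own percentage, so two different counts reached the text. A single mistyped digit would not explain it.

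**2. See which count the groups use.** 305 + 531 = 836, and 836 + 432 = 1,268. With 303 the sum is 303 + 531 = 834, which leaves two people unplaced; it closes only with 533 non-attenders, a figure that appears nowhere. The 531 is the complement of 305 within 836, so this shows that the groups were built on 305. It is not an independent count of who came.

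**3. Look for the attender rule.** The closing paragraph of Procedures ties 305 to the first session, and 305 is the size of Tx-Attender. The same section times the follow-up survey from the first session. Both attendance sentences count all 252 booster attenders among first-session attenders, and nothing mentions anyone who came only to the booster.

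**4. Size the worst case.** Suppose 303 is right and two non-attenders sit in Tx-Attender. With a true difference d between attenders and non-attenders, the Tx-Attender mean moves by d × 2/n, where n is the number analysed in that group. The contrasts with non-attenders and with controls move by that same amount. Assume d = 0.5 SD; the shift is proportional to d, so 1 SD would double it.
- Full group: 2/305 = 0.66%; 0.5 × 2/305 = 0.0033 SD.
- Time 2 data, assuming attenders respond at the arm's rate (575/836 = 68.8%) and both people responded: n = 305 × 0.688 = 210; 2/210 = 0.95%; shift 0.0048 SD. At 50% to 100% response, 2/n runs from 1.3% to 0.7%.
- Hypothesis 1, assuming also that attenders enter in proportion (415/889 = 46.7%) and that both people are included: n = 210 × 0.467 = 98; 2/98 = 2.0%; shift 0.010 SD. At 50% response, n = 71, 2/71 = 2.8% and the shift is 0.014 SD.

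A mean of 98 people has a standard error of 1/√98 = 0.10 SD, and a contrast has a larger one. A shift of 0.010 SD is at most about a tenth of that.

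**The case for a change.** The best argument for acting is that these are observed counts of one event, so no rounding tolerance excuses the difference, and a grouping variable should have a stated rule when it carries the main contrasts. The sentence that implies a first-session rule is one of the two in conflict, so it is weak evidence for its own reading. A rule counting attendance at either session could also produce a group of 305 from 303 first-session attenders. The remedy would be cheap: one look at the session records and one sentence of definition.

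The first part stands: one sentence is wrong, and the documents alone cannot prove which. The rest carries less weight. The either-session reading needs people who came only to the booster, and the text gives no sign of them. Under that reading the groups would remain 305 and 531 anyway. The evidence leans towards 305, which the groups use throughout, while the 303 sentence also misstates its own booster percentage. Only one outcome would alter an analysis: records showing 303 under the rule actually used, with groups of 303 and 533 (63.8% not attending). Even then the shift is far inside sampling error.

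**Conclusion.** No change to the plan follows. The 303/305 conflict is a clerical slip in descriptive text. The sentence giving 303 is the likelier error; if so, attendance is 36.5% rather than 36.2% and the booster rate is 82.6%, with no effect on any model. If 303 were right, the booster rate would be 252/303 = 83.2%. The missing formal definition of Tx-Attender is a gap that an analyst fills sensibly from the text, as attendance at the first session.

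The most that could be at stake is two people: 0.24 percentage points of the 836 assigned, 0.7% of Tx-Attender, and about 0.003 SD on a contrast in the full group, or about 0.01 SD in the smallest main-effect analysis. Those SD figures assume a 0.5 SD difference between attenders and non-attenders, the response rates shown, and both people misplaced and analysed. The conclusion rests on the groups having been built on 305, as both documents state. Settling the count against session records is routine checking of a report.
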